1. TRIAL OBJECTIVES

1.1. Primary effectiveness objective:

To determine whether increased postoperative surveillance in high-risk adult surgical patients reduces overall in-hospital mortality in adult surgical patients aged 18 years and over in Africa.

1.2. Secondary effectiveness objective:

To determine whether increased postoperative surveillance in high-risk adult surgical patients reduces the overall incidence of the composite of severe in-hospital complications and mortality in adult surgical patients aged 18 years and over in Africa.

2. TRIAL OUTCOME EVENTS

2.1. Primary effectiveness outcome for evaluation of increased postoperative surveillance for high-risk patients:

In-hospital death censored at 30 days if the patient is still alive and in-hospital.

2.2. Secondary effectiveness outcome:

Composite of severe in-hospital complications and death censored at 30 days if the patient is still alive and in-hospital.

Severe complications are:

- I. Superficial or deep surgical site, or body cavity infection
- II. Bloodstream infection or ARDS
- III. Urinary tract or AKI
- IV. Cardiac arrest
- V. Pneumonia
- VI. Postoperative bleed
- VII. Other severe complications

The definitions of all the secondary outcomes are given in the Appendix 1: Definitions document.

3. STATISTICAL AND ANALYTICAL METHODS

3.1 Study design

The study design is a two arm, cluster randomised trial where randomisation was stratified by hospital level (tertiary, secondary, primary) and carried out in waves to permit ongoing recruitment of hospitals throughout the duration of the trial.

3.2. Analysis population

Primary analysis will be by modified intention to treat population which includes all patients recruited from randomised hospitals where the hospital reported any patient data. Hospitals that are randomised, but do not submit any patient data will be excluded from the modified intention to treat analysis on the presumption that there is no risk of exposure to the trial intervention. Patients will be analysed in the treatment group to which their hospitals were originally allocated.

Secondary analyses will include two analytic approaches to two per protocol populations. Refer to table: Secondary analyses based on implementation fidelity. In the first per protocol analysis we will compare all patients from hospitals with data in the standard of care arm to all patients from hospitals with data in the intervention arm where the intervention hospital provided the intervention with fidelity to at least 80% of high-risk patients. Patients from hospitals in the intervention arm where the hospital delivered the intervention with fidelity to fewer than 80% of patients will be excluded from this analysis. In the second per protocol analysis we will compare all patients from hospitals with data in the standard of care arm to all patients from hospitals in the top two tertiles of implementation fidelity. Patients from intervention hospitals in the bottom tertile of implementation fidelity will be excluded from this analysis. At the hospital level we will report implementation fidelity as the proportion of high-risk patients who received the intervention with fidelity. We use two definitions for implementation fidelity; i) provision of at least the high-risk bedside guide plus one additional component of the intervention on days 0 and 1 postoperatively and ii) provision of at least 2 components of the intervention on days 0 and days 1 postoperatively, regardless whether the high-risk bedside guide is one of the components.

Secondary analyses based on implementation fidelity		
	Fidelity = High-risk individuals exposed to the bedside guide plus at least 1 additional component of the intervention	Fidelity = High-risk individuals exposed to at least 2 components of the intervention, regardless whether one is the bedside guide
Intervention hospitals where >= 80% of high-risk patients received the intervention with fidelity	Per protocol analysis 1	Per protocol analysis 3
Top two tertiles of intervention hospitals ranked according to proportion of patients receiving the intervention with fidelity	Per protocol analysis 2	Per protocol analysis 4

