Statistical analysis	The primary outcome measure is in-hospital mortality censored at 30 days of randomisation. The analysis will be conducted according to intention-to-treat principles; all participants with a recorded outcome will be analysed according to the treatment group to which they were randomised.
Recruitment start date	May 2019
Recruitment end date	March 2020
Trial duration	Until hospital discharge, censored at 30 days

3. Introduction

The non-cardiac surgical population represents a major global public health burden with approximately 234 million major surgical procedures performed worldwide each year.¹ In unselected non-cardiac surgical patients, reports of early postoperative mortality vary between 2 and 4%,^{2,3} with an annual global mortality of 5 to 10 million. Surgery is a cost-effective intervention,⁴ even in low to middle income countries⁵ and as such it is considered a core component of health.⁶ The Lancet Commission on Global Surgery was established to define safe surgery and develop strategies to ensure the adequate provision of safe surgery.⁷

Recently, the African Surgical Outcomes Study (ASOS) demonstrated, that despite a patient low risk profile and low complication rates, patients in Africa were twice as likely to die following surgery when compared to the global average.⁸ ASOS provides the most comprehensive data on surgical outcomes in Africa, comprising 25 countries, 247 hospitals, and data from over 11 000 patients.⁸ Importantly, 95% of the deaths in ASOS occurred in the postoperative period, suggesting that many lives could be saved by effective surveillance for physiological deterioration amongst the patients who developed complications.⁸ In ASOS, the median number of combined anaesthesia, surgical and obstetric specialists was 0.7 (IQR 0.2-1.9) per 100,000 population,⁸ which is well below the documented inflection point of 20 to 40 specialists per 100,000 population necessary to significantly decrease surgical mortality.⁷

It is likely that a major contributor to the high mortality in ASOS was 'failure to rescue' after a postoperative complication partly due to an inadequacy of sufficient human resources necessary to identify postoperative surgical patients at risk. A potential solution to improving surgical outcomes in Africa is identification of the high-risk surgical patient prior to further physiological deterioration.

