Not high-risk patient: (Indicate postoperative care given): Higher care ward No Yes Increased nursing observations No Yes
Assigned a bed in view of nurses' station No Yes Family with patient in ward No Yes

 High-risk patient: (Indicate all postop surveillance)	Day 0	Day 1	Day 2	Day 3	Day 4+
Higher care ward	 No  Yes				
Increased nursing observations	 No  Yes				
Assigned a bed in view of nurses' station	 No  Yes				
Family with patient in ward	 No  Yes				
'Postoperative surveillance bedside guide' at the patient's bedside?	 No  Yes				

Severe complications (tick all that apply): Superficial or deep surgical site, or body cavity infection N Y Postop day
Bloodstream infection or ARDS N Y Postop day Pneumonia N Y Postop day
Urinary tract or AKI N Y Postop day Postoperative bleed N Y Postop day
Cardiac arrest N Y Postop day Other severe complication N Y Postop day

Days in hospital after surgery

Status at hospital discharge or 30th postoperative in-hospital day: Alive & still in hospital Dead
 Alive & discharged → if alive and discharged, was patient transferred to another facility for higher care? Yes No
If deceased, photo of clinical note of death uploaded Yes CRF completed and verified by..... on dd/mm/2019

ASOS-2 unique patient ID ASOS-2 Trial CRF v4 (Intervention arm)

Patient name: _____ DOB d d m m y y y y

Patient hospital number : _____ ASOS-2 unique patient ID

Appendix 4

ASOS-2 Surgical Risk Calculator Score Card

The ASOS Surgical Risk Calculator Score card

The ASOS Surgical Risk Score is used to identify patients requiring 'increased postoperative surveillance'

How to calculate the ASOS Surgical Risk Score:

1. Calculate score before surgery using the table below
2. ASOS Surgical Risk Score = Age (points) + ASA (points) + Surgery timing (points) + Surgery severity (points) + Indication for surgery (points) + Surgery (points)
3. High-risk patients have ASOS Surgical Risk Score ≥ 10 points
4. A high-risk patient has an ASOS Surgical Risk Score ≥ 10 points
5. If ≥ 10 points, then organize 'increased postoperative surveillance' after surgery

Age	Points
18- 29	0
30-69	+1
≥ 70	+3
ASA	
ASA 1	0
ASA 2	+2
ASA 3	+5
ASA 4 and more	+8
Surgery timing	
Elective surgery	0
Urgent surgery	+3

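### Read literally, the SAP's hospital fidelity score counts high-risk patients who die or leave before day 1 as failures, so the secondary per-protocol analyses can be biased under no effect, in a direction the documents do not settle

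*Combined protocol and SAP*

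**What the plan says.** SAP 3.2 (Analysis population) gives two definitions of fidelity for a high-risk patient: "provision of at least the high-risk bedside guide plus one additional component of the intervention on days 0 and 1 postoperatively", and "provision of at least 2 components of the intervention on days 0 and days 1 postoperatively", whether or not the guide is one of them. At hospital level, "we will report implementation fidelity as the proportion of high-risk patients who received the intervention with fidelity".

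That score selects hospitals in two ways:
- Analyses 1 and 3 keep an intervention hospital only if it "provided the intervention with fidelity to at least 80% of high-risk patients".
- Analyses 2 and 4 rank the intervention hospitals: "Patients from intervention hospitals in the bottom tertile of implementation fidelity will be excluded from this analysis".

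In all four, the comparator is every standard-of-care hospital with data. Nothing is said about a high-risk patient who dies or is discharged before day 1.

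The table in the same section repeats both definitions without any day condition.

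The intervention-arm CRF (protocol Appendix 3) lets the risk score be calculated before, during or immediately after surgery. Its daily surveillance grid offers only No or Yes, with no entry for died or discharged. It also records days in hospital after surgery and "Status at hospital discharge or 30th postoperative in-hospital day".

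**The concern.** A patient who dies in theatre or on day 0 cannot have components on day 1. Because the risk score may be calculated before surgery, such a patient can already be flagged as high-risk. On the text as written, the patient lowers the hospital's fidelity score and also counts as a primary outcome event. A hospital can then be removed from the per-protocol set because of its own early deaths, and removal happens in one arm only.

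This differs from the familiar worry that hospitals delivering well also have better outcomes for other reasons. It arises from how the score is derived, and it operates even if delivery is unrelated to mortality. Case-mix adjustment would not remove it.

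At stake is the reading of analyses 1-4. After a null primary result, a distorted per-protocol relative risk could be taken as evidence that surveillance works, or does harm, where it is delivered.

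**Working it through.** **1. The plan's own figure.** Inputs from protocol 7.1 and Table 1: 2.0% against 1.5%, ICC 0.015, CV 0.63, mean cluster size 100, 80% power, two-sided 0.05.
- Individually randomised size: 10,795 per arm.
- Design effect: 1 + ((0.63² + 1) × 100 − 1) × 0.015 = 3.0803.
- Clusters: 2 × 10,795 × 3.0803 / 100 = 665.0, against 664 stated. The figure reproduces, and 332 hospitals per arm are used below.

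**2. The mechanism by hand.** A hospital delivers to 16 of 20 high-risk patients: 80.0%, kept. Add one high-risk theatre death with delivery otherwise unchanged: 16/21 = 76.2%, dropped. In a small hospital, 4/5 = 80% becomes 4/6 = 66.7%.

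**3. How common this is.** The protocol's Introduction says "95% of the deaths in ASOS occurred in the postoperative period", so 5% did not. At 100 patients and 2.0% mortality that is 100 × 0.02 × 0.05 = 0.1 such deaths per hospital, or about 33 across 332 intervention hospitals. The documents give no share for deaths on day 0.

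**4. Simulation under no effect, no day-0 discharges.** 332 hospitals per arm, gamma cluster sizes (mean 100, CV 0.63), mortality 2.0%. Gamma hospital frailty has variance 0.75, giving ICC = 0.75 × 0.02² / (0.02 × 0.98) = 0.015. Delivery is drawn independently of mortality. Assumed, not in the documents: the high-risk share of patients, 70% of deaths in high-risk patients, the delivery distribution, and the early share of high-risk deaths. The 7% row takes all theatre deaths as high-risk: 5% / 0.70 = 7.1%.

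Null relative risk (RR), 80% rule:

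| Early share of high-risk deaths | 10% high-risk, mean delivery 80%: literal / restricted | 20% high-risk, mean delivery 73%: literal / restricted |
|---|---|---|
| 7% | 0.963 / 1.002 | 0.976 / 0.998 |
| 15% | 0.909 / 1.001 | 0.947 / 1.000 |
| 25% | 0.840 / 0.999 | 0.907 / 0.999 |

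Literal means all high-risk patients are in the denominator. Restricted means only those who could be scored on day 1. The tertile rule gave 0.91-0.99 over the same range.

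A second model (beta-binomial mortality, ICC 0.015, wider assumptions: 10-30% high-risk, 50-85% of deaths high-risk, mean fidelity 0.5-0.9) gave, for the 80% rule, 0.98-1.00 at 5% early, 0.905-0.97 at 20% and 0.85-0.945 at 30%. For the tertile rule it gave 0.99-1.00, 0.93-1.00 and 0.91-0.99. The restricted score gave 0.99-1.01 throughout.

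**5. Adding day-0 discharge of high-risk survivors.** These patients fail the same rule, and the documents give no rate. Second model, 20% high-risk, 70% of deaths high-risk, mean fidelity 0.8, literal scoring:

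| Early share of deaths | Survivors discharged on day 0 | RR, 80% rule | RR, tertile rule |
|---|---|---|---|
| 5% | 0% | 0.988 | 0.991 |
| 5% | 10% | 1.019 | 1.008 |
| 5% | 20% | 1.119 | 1.027 |
| 10% | 10% | 1.002 | 1.002 |
| 20% | 0% | 0.954 | 0.968 |
| 20% | 10% | 0.951 | 0.985 |
| 20% | 20% | 0.988 | 1.003 |

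The sign depends mainly on whether the unscoreable share is larger among high-risk patients who die or among those who survive. Restricted scoring again returned about 1.00 in every row.

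**6. Effect on a two-sided 5% test (approximate).** Effective control deaths: 332 × 100 × 0.02 / 3.0803 = 215.6. If 53.5% of the intervention arm is retained and the null RR is 0.915, effective intervention deaths are 215.6 × 0.535 × 0.915 = 105.5. Then SE = √(1/215.6 + 1/105.5) = 0.119, and the false-positive rate is 11.6%. At RR 0.985 (61% retained) it is 5.2%.

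**The case against.** The strongest reply is that the SAP nowhere says an early death is scored as not delivered. That stands as a matter of wording: it is the literal consequence of the day-0-and-1 text with an all-high-risk denominator, not a stated instruction. Under the table, which has no day condition, a patient who died on day 0 after receiving the guide and one other component could count as delivered. A patient who died in theatre could not under either wording. So the conflict between text and table narrows the problem without removing it, and leaves the choice open after data are seen.

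A reader might also infer that these analyses will show a survival benefit when there is none. The documents do not support that. Day-0 discharges fail the same rule and can cancel or reverse the bias, and no discharge rate is given.

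Nor do the documents support calling the bias a large share of the planned reduction to RR 0.75. The larger values need 15-25% of high-risk deaths before day 1, which is assumed. They also use ICC 0.015, which protocol 7.1 calls conservative against 0.01 observed. At about 0.01 with no discharges, the 80% rule gives 0.97-0.98, 0.93-0.96 and 0.88-0.93 at 7%, 15% and 25% early deaths.

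Finally, the four analyses are secondary, and the primary analysis, by allocated hospital, is untouched. That limits the consequence but does not justify leaving an outcome-dependent selection rule in place when it is easily removed.

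**Conclusion.** The point holds in a conditional form. On the SAP's text, early deaths feed into the score that decides which intervention hospitals stay in per-protocol analyses 1-4, with no matching selection of control hospitals. The analyses can therefore be biased under no effect even when delivery is unrelated to mortality.

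Neither size nor direction is fixed by the documents. With no day-0 discharges, the null RR under the 80% rule is about 0.95-1.00 at the only documented anchor (5% of deaths not postoperative, from the earlier cohort). It is about 0.84-0.95 if 15-25% of high-risk deaths come before day 1. With 10-20% of high-risk survivors discharged on day 0 it can reach or pass 1, to about 1.12. The tertile rule is generally affected less, though not always: with mean fidelity 0.9, 20% early deaths and no discharges it gave 0.927, against 0.967 for the 80% rule.

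This should be corrected before analysis. It does not call the modified intention-to-treat primary result into question.

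**What to change.** In SAP 3.2 (Analysis population), for both fidelity definitions and for both the 80% cut-off and the tertile ranking:

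- Calculate hospital fidelity only among high-risk patients who were alive and still in hospital on postoperative day 1, identified from CRF status and days in hospital after surgery.
- Keep all patients, including early deaths, in the outcome analysis of every hospital that qualifies.
- Give the table the same day condition as the text.
- State whether a hospital with no scoreable high-risk patient enters the per-protocol sets.

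The cost is a few sentences in the SAP and one filter in the derivation program; the fields are already collected. The small downside is that the reported fidelity proportion no longer covers patients who died or left before day 1. The change removes this artefact only. The per-protocol results remain unprotected by randomisation and should be described that way.
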